15 CLINICAL TRIAL PROTOCOL AMENDMENTS

All appendices attached hereto and referred to herein are made part of this clinical trial protocol.

The Investigator should not implement any deviation from, or changes to the clinical trial protocol without agreement by the Sponsor and prior review and documented approval/favorable opinion from the IRB/IEC and/or notification/approval of health authorities (competent regulatory authority) of an amendment, as required by local regulation, except where necessary to eliminate an immediate hazard(s) to clinical trial patients, or when the change(s) involves only logistical or administrative aspects of the trial. Any change agreed upon will be recorded in writing, the written amendment will be signed by the Investigator and by the Sponsor and the signed amendment will be filed with this clinical trial protocol.

Any amendment to the clinical trial protocol requires written approval/favorable opinion by the IRB/IEC prior to its implementation, unless there are overriding safety reasons.

In case of substantial amendment to the clinical trial protocol, approval from the health authorities (competent regulatory authority) will be sought before implementation.

In some instances, an amendment may require a change to the informed consent form. The Investigator must receive an IRB/IEC approval/favorable opinion concerning the revised informed consent form prior to implementation of the change and patient signature should be re-collected if necessary.

## LIST OF ABBREVIATIONS AND DEFINITION OF TERMS

AE:	adverse event
AESI:	adverse event of special interest
ALP:	alkaline phosphatase
ALT:	alanine aminotransferase
ANCOVA:	analysis of covariance
APPADL:	ability to perform physical activities of daily living
AST:	aspartate aminotransferases
ATC:	anatomic category
BMI:	body mass index
BNP:	brain natriuretic peptide
CI:	confidence interval
CMH:	Cochran-Mantel-Haenszel
CSR:	clinical study report
DMC:	Data Monitoring Committee
ECG:	electrocardiogram
eCRF:	electronic case report form
FDA:	Food and Drug Administration
FPG:	fasting plasma glucose
FSH:	follicle-stimulating hormone
GGT:	gamma-glutamyl transpeptidase
HbA 1c :	glycosylated hemoglobin
HDL:	high-density lipoprotein
HLGT:	high level group term
HLT:	high level term
HR:	heart rate
hs-CRP:	high-sensitivity C-reactive protein
IMP:	investigational medicinal product
IRT:	interactive response technology
IW-SP:	Impact of Weight on self-perception
KM:	Kaplan-Meier
LDL:	low-density lipoprotein
LLN:	lower limit of normal
LLT:	lower level term
MAR:	Missing at random, Missing at random, Missing at random
MedDRA:	Medical Dictionary for Regulatory Activities
NASH:	nonalcoholic steatohepatitis
NIMP:	non-investigational medicinal product
OC:	observed cases
PCSA:	potentially clinically significant abnormality
PD:	pharmacodynamic
PK:	pharmacokinetic

PPG:	post-prandial plasma glucose
PRO:	patient-reported outcome
PSAC:	Pancreatic Safety Assessment Committee
PT:	preferred term
SAE:	serious adverse events
SAP:	statistical analysis plan
SC:	subcutaneous
SD:	standard deviation
SE:	standard error
SMPG:	self-monitored plasma glucose
SOC:	system organ class
TEAE:	treatment-emergent adverse event
ULN:	upper limit of normal
VAS:	visual analogue scale
WHO-DD:	World Health Organization-Drug Dictionary
WRSM:	weight-related symptoms measure

# 1 OVERVIEW AND INVESTIGATIONAL PLAN

## 1.1 STUDY DESIGN AND RANDOMIZATION

This is a multicenter, multinational, randomized, placebo-controlled, 7-arm parallel-group Phase 2 study. The study is double-blind with regard to SAR425899 and placebo treatments. It is open-label with regard to liraglutide comparative treatment. The volume of investigational medicinal product (IMP; ie, dose of SAR425899 or matching placebo) is not blinded.

Patients will be randomized into 1 of the 7 treatment arms:

- 3 SAR425899 treatment arms receiving 3 dose levels (60 patients per arm).
- 3 corresponding SAR425899 placebo treatment arms receiving 3 dose levels (10 patients per arm, 30 patients total).
- 1 active comparator arm receiving 1.8 mg liraglutide (60 patients).

For the biostatistical analyses, data from the 3 SAR425899 placebo arms will be pooled into 1 placebo group.

Patients will be stratified by screening visit HbA1c (<8% versus ≥8%) and Visit 4 (Day 1) body mass index (BMI: <35.0 kg/m^2 versus ≥35.0 kg/m^2).

## 1.2 OBJECTIVES

### 1.2.1 Primary objectives

The primary objective of this study is to assess the dose-response relationship of SAR425899 versus placebo in terms of glycemic control as measured by the change in glycosylated hemoglobin (HbA1c) from baseline to Week 26.

### 1.2.2 Secondary objectives

#### Main secondary objectives:

- To assess the effect of once daily dosing of SAR425899 on body weight over 26 weeks.
- To assess the safety and immunogenicity profile of SAR425899 when administered as daily subcutaneous (SC) injections over 26 weeks, including assessment of the heart rate (HR) change from baseline to Week 26 by electrocardiogram (ECG) and Holter monitor.

#### Additional secondary objectives:

- To assess the proportion of patients achieving predefined HbA1c targets of <7% and <6.5% as well as the proportion of patients achieving ≥5% and ≥10% body weight loss at Week 26.

- To assess the effect of once daily dosing of SAR425899 on additional parameters of glycemic control and lipid metabolism.
- To assess the effect of once daily dosing of SAR425899 on additional pharmacodynamic (PD) biomarkers.
- To assess the pharmacokinetic (PK) profile and parameters of SAR425899, inter-individual and inter-occasion variability in PK parameters using a population PK approach.

### 1.2.3 Exploratory objectives

- To assess and compare the safety and efficacy of SAR425899 versus liraglutide from baseline to Week 26.
- To explore SAR425899 PK/PD relationships for glycemic parameters, body weight loss and heart rate.
- To assess the treatment effects in each group on patient-reported outcomes.
- To assess the treatment effects in each group on nonalcoholic steatohepatitis (NASH) and cardiovascular biomarkers.

## 1.3 DETERMINATION OF SAMPLE SIZE

For the primary endpoint of change in HbA1c from baseline to Week 26, a sample size of 60 patients per arm of SAR425899 and 30 patients in the placebo group (pool of the 3 placebo arms) will provide 80% power to detect a difference of 0.7% in the HbA1c change from baseline to Week 26 between a dose group of SAR425899 and placebo (standard deviation (SD) 1.1%; 5% significance level 2-sided).

[figure not shown]
The total sample size will be 270 patients to be randomized over 7 arms: 3 SAR425899 treatment arms with 3 different dose levels (60 patients per arm), 3 matching SAR425899 placebo treatment arms (10 patients per arm; 30 patients total), and 1 liraglutide arm (active comparator arm with 60 patients).

For the biostatistical analyses, data from the 3 SAR425899 placebo arms will be pooled into 1 placebo group (30 patients total)

Calculations were made using nQuery Advisor® 7.0.

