
SAP version number	Date approved	Rationale	Description of statistical changes
1	This version	To be consistent with company standard.	The definition of treatment compliance was changed, with above-planned dosing defined as any day that the patient took a higher dose than planned, and under-planned dosing defined as any day that the patient took a lower dose than planned.
1	This version	Trend tests on HbA1c will be performed instead pairwise comparison of each dose of SAR425899 versus placebo for primary analysis. Same changes are also made for body weight analyses. The hierarchical testing procedure is also updated to reflect the changes.	Trend tests on HbA1c will be performed instead pairwise comparison of each dose of SAR425899 versus placebo for primary analysis. Same changes are also made for body weight analyses. The hierarchical testing procedure is also updated to reflect the changes. Details of the trend tests and hierarchical testing procedure are presented in Section 2.4.4 .
1	This version	Unblinded analyses results on body weight, HbA1c and FPG, and unblinded DMC results (including demographics, disposition, and safety summary) and additional related exploratory analyses will/may be provided to Sanofi internal project planning personnel to support compound development during the 2 interim analyses of the study.	Unblinded analyses results on body weight, HbA1c and FPG, and unblinded DMC results (including demographics, disposition, and safety summary) and additional related exploratory analyses will/may be provided to Sanofi internal project planning personnel to support compound development during the 2 interim analyses of the study. Details are presented in Section 3 .
1	This version	To account for the situation that a patient took a SAR425899/placebo dose level that is different from the planned 4 doses levels allow for the study, specify that if a patient is exposed to more than one dose level of SAR425899 since Week 8 visit or later, then the patient will be analyzed in the dose level administered on Week 8 visit or study Day 56 if Week 8 visit is not available.	Patients will be analyzed for safety analyses according to the treatment actually received. If a patient is exposed to more than one dose level of SAR425899 since Week 8 visit or later, then the patient will be analyzed in the dose level administered on Week 8 visit or study Day 56 if Week 8 visit is not available.

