##### ***Primary analysis***

The primary efficacy endpoint of change in HbA1c from baseline to Week 26 will be analyzed with missing post-baseline values imputed by placebo control-based multiple imputation (MI) method under the missing not at random framework (5, 6, 7).

- For placebo group patients, missing data will be imputed based on the placebo group data.
- For patients in the SAR425899 dose groups and liraglutide group, missing data will be imputed as if the patients were on placebo group throughout the study.

For missing HbA1c value at baseline, missing data will be imputed using MI under the missing at random (MAR) assumption. Missing data at baseline will be imputed using regression method that includes randomization stratum of screening HbA1c ( $\leq 8.0\%$ ,  $> 8.0\%$ ), randomization stratum of Visit 4 (Day 1) BMI ( $< 35.0 \text{ kg/m}^2$ ,  $\geq 35.0 \text{ kg/m}^2$ ), and baseline value in the imputation model (see sample code Part 1c in [Appendix D](#)).

The change from baseline at Week 26 values will be derived from observed or imputed Week 26 HbA1c values (see sample code Part 1a in [Appendix D](#)). Each of the complete dataset will be analyzed by the Analysis of Covariance (ANCOVA) model with treatment groups (SAR425899 0.12 mg, SAR425899 0.16 mg, SAR425899 0.20 mg, placebo and liraglutide), randomization strata of screening HbA1c value ( $< 8\%$ ,  $\geq 8\%$ ), randomization strata of Visit 4 (Day 1) BMI

(<35.0 kg/m^2, ≥35.0 kg/m^2), and country as fixed effects, and baseline HbA1c value as a covariate (see sample code Part 2 in [Appendix D](#)).

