Results from each complete dataset will be combined using Rubin's rule to provide the following. Three trend tests are planned on HbA1c. First trend test will be performed to test the hypothesis that HbA1c reduction from baseline at Week 26 increases with increase in dose. The test will be based on a contrast under the ANCOVA framework and with coefficients of +3, +1, -1, -3 and 0 for SAR425899 0.20 mg, SAR425899 0.16 mg, SAR425899 0.12 mg, placebo and liraglutide, respectively. The second trend test (SAR425899 0.16 mg versus placebo) is performed with coefficients of 0, +1, 0, -1 and 0 for SAR425899 0.20 mg, SAR425899 0.16 mg, SAR425899 0.12 mg, placebo and liraglutide, respectively. The third trend test (SAR425899 0.12 mg versus placebo) is performed with coefficients of 0, 0, 1, -1 and 0 for SAR425899 0.20 mg, SAR425899 0.16 mg, SAR425899 0.12 mg, placebo and liraglutide, respectively. Adjusted mean change in HbA1c from baseline to Week 26 for each treatment group, as well as the between-group difference (comparing each SAR425899 dose group versus placebo) and the 95% confidence interval (CI) for the between-group difference will also be provided. The overall Type 1 error for multiple comparisons of the HbA1c and body weight will be controlled by a Hierarchical testing procedure as detailed in [Section 2.4.4.3](#).

The ANCOVA model will be implemented using statistical analysis system (SAS®) (Version 9.4 or higher) MIXED procedure (PROC MIXED).

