### 2.4.4.3 Multiplicity issues

To control the type I error, a hierarchical testing procedure will be applied. The testing procedure will be performed to test the primary and secondary efficacy variables (HbA1c and body weight) by the following prioritized order. The test stop as soon as an endpoint is found not statistically significant at  $\alpha=0.05$  (2-sided).

Figure 1 - The hierarchical testing procedure

No multiplicity adjustment will be made on other secondary efficacy variables other than body weight.

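### Does SAP 1.3 need a new power figure now that a trend contrast is the first HbA1c test?

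*SAP*

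**What the plan says.** SAP 1.3 repeats protocol 11.1. With 60 patients per SAR425899 arm and 30 on pooled placebo, the trial "will provide 80% power to detect a difference of 0.7% in the" HbA1c change from baseline to Week 26, and the comparison is "between a dose group of SAR425899 and placebo (standard deviation (SD) 1.1%; 5% significance level 2-sided".

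SAP Table 2 records a change made in this version: "Trend tests on HbA1c will be performed instead pairwise comparison of each dose of SAR425899 versus placebo for primary analysis". SAP 2.4.4.1 defines the first test as a contrast "with coefficients of +3, +1, -1, -3 and 0 for SAR425899 0.20 mg", 0.16 mg, 0.12 mg, placebo and liraglutide. It continues: "The second trend test (SAR425899 0.16 mg versus placebo) is performed with coefficients" that isolate that one comparison. The third test is 0.12 mg versus placebo. The difference between 0.20 mg and placebo is still estimated with a 95% confidence interval but is not one of the three listed tests.

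SAP 2.4.4.3 sets the gate: "The test stop as soon as an endpoint is found not statistically significant at" the two-sided 5% level. The ANCOVA has treatment, the two randomization strata "and country as fixed effects, and baseline HbA1c value as a covariate". For SAR425899 and liraglutide patients, "missing data will be imputed as if the patients were on placebo group throughout the study".

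The text gives no assumed dose-response shape, no power for the contrast or for the gated steps, and no allowance for missing Week 26 values.

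**The concern.** The only power figure in the SAP belongs to a pairwise test that no longer opens the sequence. The primary objective is dose-response and the trend contrast now addresses it, so a reader could attach the 80% to a test for which it was not calculated. A linear contrast has power that depends on the shape of the dose-response, which a single pairwise figure cannot show. It also gates the two remaining HbA1c dose tests.

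Two further gaps sit beside this. SAP 1.3 does not say whether SD 1.1 is before or after adjustment for baseline HbA1c. The total of 270 equals 3 × 60 + 30 + 60, so nothing is added for missing Week 26 values, although missing active-arm values are imputed as placebo. If the first test were well below 80%, the trial could miss its primary objective more often than the plan suggests.

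**Working it through.** **Inputs** (SAP 1.3 and 2.4.4.1): 60 per dose, 30 placebo, SD 1.1, effect 0.7, two-sided 5%, contrast +3/+1/-1/-3. The dose-response shapes, missing rates and correlations below are assumptions, because the documents give none. Power is the probability that a noncentral t, with noncentrality (effect ÷ SE), exceeds its 97.5% critical value.

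**The plan's own figure.** SE = 1.1 × √(1/60 + 1/30) = 0.246. Noncentrality = 0.7/0.246 = 2.85. With 60 + 30 - 2 = 88 degrees of freedom, power = 80.4%. With the five-group residual, 270 - 5 = 265 degrees of freedom, it is 80.9%. The stated 80% reproduces.

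**The trend contrast.** SE = 1.1 × √((9 + 1 + 1)/60 + 9/30) = 0.765. With d the effect of each dose versus placebo, the contrast is 3·d(0.20) + d(0.16) - d(0.12).
- Flat 0.7: 2.10 + 0.70 - 0.70 = 2.10; 2.10/0.765 = 2.75; power 78.1%.
- Dose-proportional (0.42, 0.56, 0.70 for 0.12, 0.16, 0.20 mg): 2.10 + 0.56 - 0.42 = 2.24; 2.24/0.765 = 2.93; power 83.1%.

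**The gated steps.** The three SAP statistics are correlated 0.75 (trend, 0.16 mg), 0.54 (trend, 0.12 mg) and 0.67 (0.16 mg, 0.12 mg). Joint power comes from 1,000,000 simulated draws of correlated t statistics with 265 degrees of freedom. For comparison, the protocol's pairwise step-down is assumed to run 0.20, 0.16, 0.12 mg. Each chain shows the probability of passing step 1, steps 1 and 2, and all three, for HbA1c only.

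| Assumed effect at 0.12/0.16/0.20 mg | SAP chain | Protocol chain | Step 1 difference |
|---|---|---|---|
| 0.70/0.70/0.70 | 78/71/65% | 81/72/66% | -3 |
| 0.42/0.56/0.70 | 83/60/34% | 81/58/34% | +2 |
| 0.23/0.47/0.70 | 86/47/14% | 81/45/14% | +5 |
| 0.35/0.70/0.70 | 89/78/28% | 81/72/28% | +8 |
| 0.70/0.80/0.90 | 95/88/76% | 95/88/77% | 0 |
| 0.70/0.70/0.50 | 50/48/45% | 53/50/48% | -3 |

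First-test power moves by about -3 to +8 points. The later steps are nearly the same under both plans wherever step 1 is. In the dose-proportional case the ungated power is already only 62% for 0.16 mg and 40% for 0.12 mg, so the fall to 60% and 34% mostly reflects the assumed effects.

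**Missing Week 26 values.** Multiply every effect by (1 - m), with no effect retained and the SE held fixed. For m = 5/10/15%, the flat trend test has 74/69/64%, the dose-proportional trend test 79/75/70%, and the pairwise test behind the 80% has 76/72/67%. All three fall together.

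**Meaning of SD 1.1.** If it is before adjustment and the baseline-change correlation is r, the working SD is 1.1 × √(1 - r²): 1.05 at r = 0.3 and 1.01 at r = 0.4. The flat trend test then has 82% or 85%.

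**The case for a change.** The strongest case for a change is that the SAP revised its first test and its hierarchy and left the power statement alone. If every dose has exactly the design effect, the new first test is just under 80%, passing all three HbA1c steps is 65%, and the shape dependence is hidden. A downturn at the top dose would halve the odds of opening the gate. A few sentences in SAP 1.3 would cure this at almost no cost.

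The facts stand, but the consequence does not follow:
- SAP 1.3 names its comparison, Table 2 announces the switch and 2.4.4.1 lists every coefficient. A statistician can see that the 80% is not the contrast's power and can compute that power from what is printed.
- The downturn hurts the pairwise test of 0.20 mg almost as much (53% against 50%). It is a property of starting at the top dose, not of the contrast.
- Step-down testing and placebo-based imputation are already in protocol 11.4.2.3 and 11.4.2.1.1. The missing-data and SD points apply equally to protocol 11.1 and pull in opposite directions. SAP 2.4.4 also keeps values after discontinuation or rescue, and 2.5.4 can allocate a late discontinuation-visit value to Week 26, so missing values should be fewer than discontinuations.
- SAP 1.5 dates the first enrolment to December 2016 under the original protocol. The statement in SAP 1.3 records why 270 was chosen, and a SAP may fairly repeat it. Any added table would rest on shapes and missing rates that its author picks.

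**Conclusion.** The concern is accurate as an observation but calls for no change. The 80% is right for one dose versus pooled placebo with complete data (80.4%). The contrast that now comes first has 78% power under a flat 0.7 effect and 83% to 95% under the rising shapes tabulated, a shift of roughly -3 to +8 points from a pairwise first test. That is neither an arithmetic error nor evidence that the trial is underpowered. It is a small reporting gap that a reader can fill from the coefficients and group sizes given. Filling it in the SAP would leave enrolment, testing order, estimates and conclusions as they are.

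This rests on SD 1.1, complete data and no covariate gain for the headline figures, and on assumed dose-response shapes. The HbA1c order is taken from SAP 2.4.4.1. The testing figures in protocol 11.4.2.3 and SAP 2.4.4.3 could not be read in the copy reviewed. If body weight tests sit between the HbA1c steps, the gated figures change, but the first-test figure does not as long as the trend test opens the sequence.

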### 1.4 STUDY PLAN

\* depending on the SAR425899/placebo dose regimen

SAR425899 and matching placebo: low dose regimen = 0.06 (1 week) – 0.12 mg (25 weeks)

mid dose regimen = 0.06 (1 week) – 0.12 (1 week) – 0.16 mg (24 weeks)

and high dose regimen = 0.06 (1 week) – 0.12 (1 week) – 0.16 mg (1 week) – 0.20 mg (23 weeks)

Liraglutide: 0.6 mg (1 week) – 1.2 mg (1 week) – 1.8 mg (24 weeks)

## 1.5 MODIFICATIONS TO THE STATISTICAL SECTION OF THE PROTOCOL

This section summarizes major changes to the protocol statistical section with emphasis on changes after study start (after the first patient was enrolled).

The protocol history table below gives the timing, rationale, and key details of major changes to the protocol statistical section.

The first patient was enrolled on Dec 23rd, 2016 under the original protocol. The amendment 1 was finalized on Jan. 23rd, 2017. The body weight interim analysis is planned on Sept. 2017 and the interim analysis for PK/PD is planned on Dec. 2017. Note that the interim analysis for PK/PD was added on amendment 1.

**Table 1 - Protocol amendment statistical changes**

Amendment Number	Date Approved	Rationale	Description of statistical changes
1	23-Jan-2017	
Increased urinary free-cortisol level was observed in animal studies of SAR425899 but the relevance of this finding to human is unclear. The Food and Drug Administration (FDA) requested to add the measurement of urinary free-cortisol and creatinine from 24h urines at baseline and end of treatment in order to assess the increase in urinary free-cortisol in humans which may suggest a potential effect of SAR425899 on the hypothalamic-pituitaryadrenal axis.
 
In phase I studies an increase of ketones bodies was observed for the SAR425899 high dose group (up to 0.18 mg) but not for placebo and the SAR425899 low dose group. In view of the currently requested administration of up to 0.20 mg of SAR425899 and the potential gastrointestinal side effects together with the simultaneous administration of metformin, the BfArM recommended to consider metabolic acidosis as an adverse event of special interest with an immediate notification in order to recognize this state very early in the study and to discontinue the administration of metformin when applicable.
 
Leptin and microRNA were initially considered as biomarkers of interest in this study. Leptin plasma concentrations are correlated with fat mass. MicroRNA is a surrogate biomarker for nonalcoholic steatohepatitis (NASH). Thus assessment of these two biomarkers was expected to provide information about SAR425899 effect on fat mass and NASH. However the sponsor decided to not measure these parameters anymore during this phase II study. For Leptin, it is not required for any modeling and is not recommended as a surrogate to test for differences in energy expenditure. Nevertheless Leptin and fat mass changes are planned to be assessed in a study dedicated to energy expenditure assessment. For MicroRNA, patients included in this study are not diagnosed for NASH and no liver biopsy is taken which could make the interpretation of microRNA results difficult. Nevertheless microRNA is planned to be assessed in a study dedicated to NASH.
	
To add urinary free-cortisol and creatinine measured in 24 hours urines at baseline and in Visit 12 (Week 26, End of treatment).
 
To add metabolic acidosis as a new adverse event of special interest as requested by the BfArM.
 
To remove Leptin and microRNA assessments

Amendment Number	Date Approved	Rationale	Description of statistical changes
1	23-Jan-2017	
Potentially an interim analysis for population PK and PK/PD will be performed for 60% completers, in order to have data for internal project planning purposes.
 
To change the reference timepoint for blood sampling during the meal test from the end of the standardized meal to the start of the standardized meal and change the time period for the standardized meal consumption from 15 minutes to 10 minutes.
 
TSH, T3 and FT4 measurements will be performed at baseline and endpoints visits in order to assess further the thyroid function during the study.
	
To add a potential interim analysis for 60% completers
 
To add Amylase/lipase assessment in Visits 9 and 11 as requested by the BfArM.
 
Correction of a discrepancy between the text in Section 9.2.1.2.2 and Table 2 regarding the reference time for blood sampling during the meal test.
 
To Add thyroid function assessment at baseline and endpoint visits.

